## **7.3 Reporting of SAEs and Unexpected Adverse Reactions**

The Qualified Investigator will be responsible for classification of an AE as an SAE within 24h of notification. Causality should be signed off by the Qualified Investigator prior to reporting to ethics and regulatory bodies. Notification of any serious adverse events must be made in writing to the study sponsor. The IRB will be notified of all SAEs and unexpected adverse reactions. All SAEs will be reported to the Therapeutics Products Directorate (TPD) in an expedited manner.

The sponsor must notify the TPD of all serious adverse reactions as follows:

- a) If it is neither fatal or life threatening, within 15 calendar days after the day on which the sponsor becomes aware of the information; and

- b) If it is fatal or life threatening, must be reported as soon as possible, but not later than seven (7) days after the day on which the sponsor becomes aware of the information.

## 8 STATISTICAL EVALUATION

### 8.1 Determination of sample size

This is a pilot test and no calculation was conducted for sample size.

### 8.2 Study Population

- The **Safety Population** will consist of all participants who received any amount of either product, and on whom any post-randomization safety information is available.
- The **Per Protocol (PP) Population** consists of all participants who do not have any major protocol violations and complete all study visits and procedures connected with measurement of the primary variable.

### 8.3 Analysis Plan

The primary outcome variable will be the peak plasma ascorbic acid level ( $C_{MAX}$ ). The responses from all time points will be compared to determine the time at which the plasma ascorbic acid level reaches its peak ( $T_{MAX}$ ). For each product, a one sample t-test will be utilized to test whether the mean peak plasma ascorbic acid level is greater than 37  $\mu\text{M}$ .

$$H_0: C_{MAX} \leq 37 \mu\text{M}$$

$$H_A: C_{MAX} > 37 \mu\text{M}$$

Because the plasma ascorbic acid level reaches a saturation point at approximately 80  $\mu\text{M}$  (9;10), some of the participants may reach saturation at the peak time. Depending on the proportion of participants who peak at saturation level, a one sample t-test may be inappropriate and nonparametric techniques may be required to judge the typical peak plasma ascorbic acid level for each product.

The action standard for each product will be that the typical peak plasma ascorbic acid level is statistically significantly greater than 37  $\mu\text{M}$  and each product which meets the action standard will be determined to have provided an effective dose.

Additional outcome variables which will be measured include the ascorbic acid level in white blood cells and the ascorbic acid level in urine. These data will be collected for informational purposes only.

Descriptive statistics will be provided for participant demographic and baseline characteristics. Line graphs showing the individual and mean concentrations in  $\mu\text{M}$  of plasma, WBC and urine ascorbic acid over the 24 h will be provided for the investigational products.

Pharmacokinetic parameters, including the incremental area under the curve (iAUC0-24h and iAUC0-∞), the maximum observed concentration (Cmax) time, and maximum concentration (Tmax) will be calculated for each participant. The area under the curve parameter will be calculated using the trapezoid approximation from 0h to 24h and by using the exponential decay approximation for 24h to infinity.

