### 3 STUDY DESIGN

This will be a randomized, examiner-blind, cross-over, comparator-controlled bioequivalence study.

The planned sample size for this study is 30 participants to complete (equal number of males and females). Assuming 20% drop-out rate from enrollment to completion, 36 participants will be randomized equally to each of the two study arms in an examiner-blind manner at a ratio of 1:1.

Study Arm	Participant Number*
Gummy → Comparator	N = 18
Comparator → Gummy	N = 18
Total	N = 36

\*Assumed 20% drop-out rate from enrollment to completion

To evaluate study outcomes, assessments will be conducted at screening, baseline and, all study visits.

The study will be conducted at a single site in KGK Synergize, [REDACTED].

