##### **Removal by Qualified Investigator:**

Participant discontinuation should be considered at the discretion of the Qualified Investigator. The circumstances of any discontinuation must be documented in detail in the participant file and final report. If possible, the evaluations planned for the end of study will be carried out at the time when the participant is withdrawn from the study. A participant leaving the study prematurely will be replaced by another if required to ensure 30 participants complete the study. It is understood by all concerned that an excessive rate of withdrawals can render the study uninterpretable; therefore, unnecessary withdrawal of participants should be avoided.

Criteria for removal of participants from the study will include:

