#### **6.6 Visit 4 – Clinic Day 3 (Test Period 2, 8h In-Clinic Day)**

Participants will return to the clinic, after fasting for 12 hours (water is allowed), for the second test period assessments. Study diaries will be collected and new diaries dispensed.

Clinic Day 3 assessment includes:

- Reviewing of concomitant therapies, adverse events, and current health status
- Collecting 7-day food diary food record and reviewing dietary compliance
- Recording weight and BMI
- Recording seated resting blood pressure and heart rate
- Pre-dose blood will be collected for the analysis of CBC, electrolytes (Na, K, Cl), creatinine, eGFR, AST, ALT, and bilirubin
- Blood collection (plasma and WBC) for pre-dose (baseline, 0h) analysis of L-ascorbic acid
- Pre-dose urine collection (baseline, 0h) and total urine volume will be recorded and a sample for L-ascorbic acid analysis will be retained
- Administration of the investigational product that the participant did not receive in round 1 with 250 mL of room temperature water. Participants who receive the gummies will be instructed to chew gummies thoroughly before swallowing. Time of consumption will be recorded. Water will be permitted ad libitum 1 hour after dosing.
- Participants will be instructed to avoid reclining for 2 hours after dosing.
- Blood collection (plasma and WBC) for post-dose analysis of L-ascorbic acid at 30min 1h, 2h, 3h, 4h, 5h, 6h, 8h, 10h and 12h post-dose
- Urine collection between 0-2h post-dose and total volume will be recorded.
- Sample of 0-2h post dose urine will be retained for L-ascorbic acid analysis
- Urine collection between 2-4h post-dose and total volume will be recorded.
- Sample of 2-4h post dose urine will be retained for L-ascorbic acid analysis
- Urine collection between 4-8h post-dose and total volume will be recorded
- Sample of 4-8h post-dose urine will be retained for L-ascorbic acid analysis
- Urine collection between 8-12h post-dose and total volume will be recorded
- Sample of 8-12h post-dose urine will be retained for L-ascorbic acid analysis
- Recording of adverse events

Standardized meals devoid of vitamin C containing products will be provided to participants in the clinic (Refer to appendix 4). The following meals will be provided at the clinic: Breakfast after the 2h blood sampling, lunch after the 5h blood sampling, and supper between the 6h and 12h sampling. All food items and quantities consumed will be recorded by clinic staff for each individual participant.

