### **8.3.1 Premature Discontinuation Description**

For each premature discontinuation, the following parameters will be listed: participant number, dates of start and end of supplementation, and the reason of premature discontinuation. If a participant is withdrawn or drops out of the pharmacokinetic study, KGK will replace the participant to ensure a total number of 30 participants complete the study.

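### Each product's Cmax test pools the two periods and ignores the randomised sequence: mildly conservative if the periods differ, with a small shift in the descriptive product means if completers are unequal by sequence

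*Combined protocol and SAP*

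**What the plan says.** Section 3 describes a randomised cross-over with two orders, gummy first or comparator first: "Assuming 20% drop-out rate from enrollment to completion, 36 participants will be randomized equally to each of the two study arms", 18 to each. Section 6.6 gives the second dosing as: "Administration of the investigational product that the participant did not receive in round 1". Each product is therefore taken in period 1 by one sequence and in period 2 by the other.

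The primary variable in section 8.3 is peak plasma ascorbic acid. The planned analysis reads: "For each product, a one sample t-test will be utilized to test whether the mean peak plasma ascorbic acid level is greater than" 37 µM. The success rule is: "The action standard for each product will be that the typical peak plasma ascorbic acid level is statistically significantly greater than 37" µM. An unnamed nonparametric technique may replace the t-test if many participants peak at saturation, put at about 80 µM. Section 8.3 also plans mean curves by product and per-participant pharmacokinetic parameters. Section 8 contains no period, sequence or carry-over term.

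The replacement rules in sections 4.4 and 8.3.1 aim at a number of completers and do not mention sequence; section 8.3.1 says "KGK will replace the participant to ensure a total number of 30 participants complete the study". Section 3 asks for balance among completers by sex only. In Appendix 5 the first 18 numbers on each sex list split 9 A-first and 9 B-first, so allocation itself is balanced.

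**The concern.** A one-sample t-test treats all of a product's values as one homogeneous sample. Here they are two groups, defined by the randomised sequence and measured on different occasions. Period 1 follows about 7 days of restricted diet. Period 2 follows a further 7 to 9 days of restriction and an earlier dose of the other product. Section 8.3 states no baseline subtraction for Cmax, so a change in pre-dose level between periods could pass into the primary variable.

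Two things would follow from a period difference. The pooled standard deviation would contain between-period spread that the design allows one to remove. And if completers were unequal by sequence, each product's mean would lean towards the period in which more participants took it, with gummy and caplet leaning in opposite directions. Every listed outcome in section 2 pairs gummy with caplet, so readers will look at the two means side by side even though section 8.3 plans no test between them.

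**Working it through.** **Inputs.** From the documents: 30 completers, 36 randomised, 18 per sequence, null value 37 µM, one-directional alternative. Not given, so assumed: one-sided alpha 0.05; SD of Cmax within a period (s) 10 to 20 µM; period difference (d) 5 to 10 µM; true mean 37 to 60 µM; 6 of 36 lost at random.

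**The plan's own figure.** 30 × 1.20 = 36, as stated.

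**1. Widening at 15:15.** The pooled variance is s² + (d²/4)(30/29).
- d = 0.5 s: 1 + 0.0625 × 1.0345 = 1.065, square root 1.032. The standard error is 3% too large.
- d = s: 1 + 0.25 × 1.0345 = 1.259, square root 1.122. The standard error is 12% too large, and 30 completers act like 30/1.259 = 23.8.

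**2. Imbalance among completers.** The number lost from one sequence is hypergeometric (36, 18, 6), with variance 6 × 0.5 × 0.5 × 30/35 = 1.286 and SD 1.134. The split probabilities are 0.34 for 15:15, 0.48 for 16:14, 0.16 for 17:13 and 0.02 (0.019) for 18:12.

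**3. Shift in the descriptive means.** A product's mean departs from its equal-period mean by d(n2/n − 0.5), where n2 is the number taking it in period 2. The other product moves by the same amount the other way, so the gap is d(n2 − n1)/n. Its SD is 2 × 1.134/30 = 0.076 d and its maximum is 6/30 = 0.20 d. At d = 10 µM that is an SD of 0.76 µM and a maximum of 2 µM.

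**4. Does the shift inflate the error of the 37 µM test?** Over random losses it adds (1.134/30)² d² = 0.0014 d² to the variance of a product mean. The pooled squared standard error already carries about d²/(4 × 29) = 0.0086 d², six times as much. Simulation at a true mean of 37 µM with random losses (200,000 runs) gives type I error of 0.046 (s 10, d 5), 0.036 (s 10, d 10), 0.043 (s 15, d 10) and 0.045 (s 20, d 10). The sequence-adjusted test gives 0.050 to 0.051 in the same settings.

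**5. Power at 15:15, d = 10 µM.**

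| True mean (µM) | s (µM) | Planned | Sequence-adjusted |
|---|---|---|---|
| 42 | 10 | 0.80 | 0.85 |
| 42 | 15 | 0.52 | 0.56 |
| 42 | 20 | 0.36 | 0.38 |
| 45 | 15 | 0.87 | 0.89 |
| 50 | 20 | 0.96 | 0.97 |
| 60 | 20 | 1.00 | 1.00 |

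The largest gain in the table is 5 points, at d = s. At one-sided alpha 0.025 that row reads 0.67 against 0.75.

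**The case against.** The strongest reply is that this is an efficiency refinement in a self-described pilot with no sample-size calculation, and that the primary verdict does not depend on it. Most of that stands. The introduction gives a plasma half-life of at most 8 hours, so a 7-day washout is at least 168/8 = 21 half-lives and direct plasma carry-over is negligible. Both periods follow a restricted-diet washout and a 12-hour fast. Longer restriction would lower period 2 while an earlier dose would raise it, so even the sign of d is unclear. AUC is specified as incremental; if that means baseline-corrected, a period shift in baseline is largely removed from it.

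Three stronger readings are tempting, and the documents do not support them.

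- **That the planned test has an inflated false-positive rate.** Type I error does reach 0.064 to 0.099 (s 10 to 20, d 5 to 10 µM) when 18 of 30 take a product in the higher period. For a given product that split has probability 0.0095 under random loss, and 12 of 30 gives 0.009 to 0.037. Over random losses the rate stays below nominal.
- **That the plan will produce a false product difference.** Section 8.3 tests each product against 37 µM and has no gummy-caplet test. The shift affects description only, and the 0.20 d figure is an extreme.
- **That the replacement rule is the cause.** It is silent on sequence, but the imbalance above arises from losses alone. The documents do not show that replacement makes it worse, and equal period weighting deals with it either way.

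What remains is that the analysis ignores the factor that was randomised, when using it costs almost nothing.

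**Conclusion.** The omission is real and its consequence is small. A period difference makes the planned test mildly conservative and can move the two descriptive means apart by a small fraction of d. The verdict against 37 µM would be sensitive to this only if true mean Cmax lay within a few µM of the threshold and d were large relative to the SD; well above it, at 60 µM, nothing changes. These sizes rest on assumed values of d, SD, true mean and alpha, none of which the documents give, and on losses unrelated to sequence. This is an optional improvement and does not change the primary conclusion.

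**What to change.** In section 8.3:

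- For each product, regress Cmax on sequence coded -1/+1 and test the intercept against 37 µM on n-2 degrees of freedom. The intercept is the equal-weight average of the product's two period means.
- If the nonparametric fallback is used, name it and stratify it by sequence.
- Report product means, including those of AUC and the mean curves, with equal period weights.
- Show 0 h plasma ascorbic acid by period. These samples are already collected at Visits 2 and 4.

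**Cost.** SAP wording and one degree of freedom: with 30 completers the one-sided 5% critical value goes from 1.699 to 1.701. If there is no period difference, equal weighting costs nothing more at 15:15. At 18:12 the standard error is s × √((1/18 + 1/12)/4) = 0.1863 s instead of s/√30 = 0.1826 s, about 2% larger. No new data or participants are needed.

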### **8.3.1 Premature Discontinuation Description**

For each premature discontinuation, the following parameters will be listed: participant number, dates of start and end of supplementation, and the reason of premature discontinuation. If a participant is withdrawn or drops out of the pharmacokinetic study, KGK will replace the participant to ensure a total number of 30 participants complete the study.

### **8.3.2 Safety**

For adverse events, a descriptive analysis will be given. Adverse events will be presented in a frequency table by category and investigational product. Furthermore, description, frequency, severity and causality will be reported for each adverse event.

Continuous safety parameters (e.g. hematology, clinical chemistry, heart rate and blood pressure) will be summarized using a table including mean, standard deviation, median, minimum value, and maximum value for each measurement point. The changes from baseline will also be summarized similarly.

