### **Safety outcomes:**

1. The difference in vital signs, hematology and clinical chemistry parameters between the gummy formulation vs. that of a comparator product
2. The difference in the incidence of adverse events between the gummy formulation vs. that of a caplet comparator product

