# 6 STUDY ASSESSMENTS

See Appendix 1 for the schedule of assessments and procedures, and Appendix 1a for time points for blood and urine sampling:

- Table 1A: A total of twelve (12) time points for blood sampling including baseline prior to dosing at 0h, and 0.5, 1, 2, 3, 4, 5, 6, 8, 10, 12 and 24 h post dosing for ascorbic acid analysis.
- Table 1B: A total of four time points for blood safety parameters.
- Table 1C: A total of six time points for urine ascorbic acid.

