## **6.3 Visit 2 – Baseline: Clinic Day 1 (Test Period 1, 8h In-Clinic Day)**

Eligible participants will return to the clinic after fasting for 12 hours (only water is allowed) for baseline assessments.

Baseline assessments include:

- Reviewing of concomitant therapies and current health status
- Physical exam
- Assessing of inclusion and exclusion criteria
- Collecting 7-day food record and reviewing dietary compliance
- Randomizing eligible participants

- Recording weight and BMI
- Recording seated resting blood pressure and heart rate
- Blood collection (plasma and WBC) for pre-dose baseline (0h) analysis of L-ascorbic acid
- Pre-dose urine collection (baseline 0h) and total urine volume will be recorded and a sample for L-ascorbic acid analysis will be retained
- Following randomization and collection of pre-dose samples, Investigational product administration with 250 mL of room temperature water and recording of consumption time. Participants who receive the gummies will be instructed to chew gummies thoroughly before swallowing. Water will be permitted ad libitum 1-hour after dosing.
- Participants will be instructed to avoid reclining for 2 hours after dosing.
- Blood collection (plasma and WBC) for post-dose analysis of L-ascorbic acid at 30min, 1h, 2h, 3h, 4h, 5h, 6h, 8h, 10h and 12h post-dose
- Urine collection between 0-2h post-dose and total volume will be recorded.
- Sample of 0-2h post dose urine will be retained for L-ascorbic acid analysis
- Urine collection between 2-4h post-dose and total volume will be recorded.
- Sample of 2-4h post dose urine will be retained for L-ascorbic acid analysis
- Urine collection between 4-8h post-dose and total volume will be recorded
- Sample of 4-8h post dose urine will be retained for L-ascorbic acid analysis
- Urine collection between 8-12h post-dose and total volume will be recorded
- Sample of 8-12h post dose urine will be retained for L-ascorbic acid analysis
- Recording of adverse events

Standardized meals devoid of vitamin C containing products will be provided to participants in the clinic (Refer to appendix 4). The following meals will be provided at the clinic: Breakfast after the 2h blood sampling, lunch after the 5h blood sampling, and supper between the 6h and 12h sampling. All food items and quantities consumed will be recorded by clinic staff for each individual participant.

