#### **6.4 Visit 3 – Clinic Day 2 (Test Period 1, 24h Assessment)**

Participants will return to the clinic for the 24h post-dose sample collections.

- Study diary will be collected and a new diary dispensed
- Concomitant therapies and adverse events will be reviewed
- Food record will be collected and dietary compliance will be reviewed
- Weight, BMI, seated resting blood pressure and heart rate will be recorded
- Urine containers will be collected, total urine volume will be recorded and a sample for L-ascorbic acid analysis will be retained
- 24h post-dose blood sample (plasma and WBC) will be collected for the analysis of L-ascorbic acid
- Blood collection for the analysis of CBC, electrolytes (Na, K, Cl), creatinine, eGFR, AST, ALT, and bilirubin
- 7-day food records will be dispensed to record all intake of between now and their next visit

Prior to leaving the clinic participants will be reminded to maintain compliance and refrain from consuming St. John's Wort, other health supplements, foods and beverages containing vitamin C (Appendix 2) and high caffeine, alcohol, grapefruit and grapefruit juice. Participants will be reminded to maintain similar levels of physical activity throughout the study.

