## 6.9 Sample collection and Processing (Appendix 6 for Flow Chart)

Blood samples will be drawn from the participants at screening (Visit 1), baseline visit (Visit 2, Day 0), visit 3, visit 4 and at the end-of-study visit (visit 5) as indicated in the schedule of assessments.

Protection of volunteer confidentiality will extend to all data generated from the assaying of these samples. These samples will be alphanumerically coded and the persons (examiner blinded) performing the analysis will not be aware of the participant's identity or the allocated product they received.

Blood collected for the analysis of CBC, electrolytes (Na, K, Cl), creatinine, eGFR, AST, ALT, and bilirubin will be delivered to LifeLabs [REDACTED].

The collected whole blood will be processed to generate plasma and WBC for vitamin C analysis. Plasma and WBC will be separated and stored in light resistant cryogenic tube and stored at -80°C. Plasma samples will be delivered on dry ice to LifeLabs [REDACTED]. WBC samples will be delivered on dry ice to Mount Sinai laboratory in [REDACTED]. Stability of non-acidified vitamin C at -80°C is up to 21 days. Retainer samples will be stored at -80°C.

Urine collected for vitamin C analysis will be aliquoted into light resistant cryogenic tubes and stored at -80°C. Urine samples will be delivered on dry ice to Mount Sinai laboratory [REDACTED]. Stability of non-acidified vitamin C at -80°C is up to 21 days. Retainer samples will be stored at -80°C.

Blood Collection:

At screening (Visit 1), 13 mL of whole blood will be collected in:

1. Two 4 mL EDTA vacutainer tubes to generate plasma for:
  - a. CBC analysis (1 tube)
  - b. Hb1Ac analysis (1 tube)
2. One 5 mL SST vacutainer tube to generate serum for:
  - a. electrolytes (Na, K, Cl), creatinine, eGFR, AST, ALT, and bilirubin analysis (1 tube)

At baseline (Visit 2), 176 mL of whole blood will be collected in:

1. Twenty-two 8 mL sodium-heparin CPT™ vacutainer tubes to generate plasma and WBC for:
  - a. L-ascorbic acid analysis (total of 22 tubes – 2 tubes per time point: pre-dose (0h), 30min, 1h, 2h, 3h, 4h, 5h, 6h, 8h, 10h, and 12h post-dose)

Visit 3, 25 mL of whole-blood will be collected in:

1. One 4 mL EDTA vacutainer tube to generate plasma for:
  - a. CBC analysis (1 tube)
2. One 5 mL SST vacutainer tube to generate serum for:
  - a. electrolytes (Na, K, Cl), creatinine, eGFR, AST, ALT, and bilirubin analysis (1 tube)

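### Section 8.3.2 summarises laboratory and vital-sign data by measurement point with no split or difference by product, so safety outcome 1 has no planned analysis; the laboratory baseline is also undefined

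*Combined protocol and SAP*

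**What the plan says.** Section 2 lists as safety outcome 1: "The difference in vital signs, hematology and clinical chemistry parameters between the gummy formulation vs. that of a comparator product". Outcome 2 is the matching comparison for adverse events.

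Section 8.3.2 treats the two kinds of data differently. For events: "Adverse events will be presented in a frequency table by category and investigational product". For continuous parameters it plans the mean, standard deviation, "median, minimum value, and maximum value for each measurement point", and then: "The changes from baseline will also be summarized similarly". It mentions no product, no difference and no interval for the continuous data, and it does not say which sample is the baseline.

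On when the data are collected:

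- Section 6: "A total of four time points for blood safety parameters". Table 1B in Appendix 1a places these at Visits 1, 3, 4 (pre-dose) and 5.
- Section 6.9: "At baseline (Visit 2), 176 mL of whole blood will be collected in" 22 tubes, all for ascorbic acid.
- Section 6.4 (Visit 3, 24 h after the first dose): "Blood collection for the analysis of CBC, electrolytes (Na, K, Cl), creatinine, eGFR, AST, ALT, and bilirubin". Section 6.7 repeats this at Visit 5, 24 h after the second dose.
- Section 6.3 (Visit 2) includes "Recording seated resting blood pressure and heart rate", and section 6.6 does the same at Visit 4. Both list it ahead of dosing. Vital signs are taken again at Visits 3 and 5.

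**The concern.** In a two-period cross-over, a visit does not identify a product. At Visit 3, half the participants are 24 h after the gummy and half are 24 h after the caplet; at Visit 5 the halves are exchanged. A summary indexed only by measurement point therefore averages over the factor that safety outcome 1 asks about. If the tables are built from the text as it stands, the report will list a between-product outcome and contain nothing that estimates it.

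The omission is hard to put down to a convention left unsaid. The plan names product when it means product: for adverse events in the same section, and in section 8.3 for the test on peak plasma level and for the concentration graphs.

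A second, separate point concerns laboratory change from baseline. The visit called Baseline has no safety sample, so the reader of a change table cannot tell what the change is measured from, or whether it means the same thing in both periods.

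**Working it through.** **1. Which visits have safety blood.** Tube counts and sizes are from section 6.9.

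| Visit | Tubes | mL | of which safety |
|---|---|---|---|
| 1 (screening) | 2×4 + 5 | 13 | 13 |
| 2 (Baseline) | 22×8 | 176 | 0 |
| 3 (24 h, period 1) | 4 + 5 + 2×8 | 25 | 9 |
| 4 (pre-dose and 0–12 h, period 2) | 4 + 5 + 22×8 | 185 | 9 |
| 5 (24 h, period 2) | 4 + 5 + 2×8 | 25 | 9 |

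The sum is 13 + 176 + 25 + 185 + 25 = 424 mL, which reproduces the plan's stated total. The ascorbic acid tubes use up the whole Visit 2 volume, so no safety tube is hidden there.

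**2. How products fall across visits.** Section 3 gives 18 participants per sequence. In Appendix 5, the first 18 numbers of each list (the last two are not used) give 9 A-first and 9 B-first among males and the same among females, so 18:18 overall.

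**3. What a table by visit can show.** Let the 24 h mean be μ + d after the gummy and μ after the caplet. Let g participants be gummy-first and c caplet-first. Ignoring any period effect:

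- Visit 3 mean = μ + d·g/(g + c)
- Visit 5 mean = μ + d·c/(g + c)
- Visit 3 − Visit 5 = d·(g − c)/(g + c)

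| g : c | Visit 3 shift | Visit 5 shift | Share of d in the visit contrast |
|---|---|---|---|
| 18 : 18 | 0.500 d | 0.500 d | 0 |
| 15 : 15 | 0.500 d | 0.500 d | 0 |
| 16 : 14 | 0.533 d | 0.467 d | 2/30 = 7% |
| 17 : 13 | 0.567 d | 0.433 d | 4/30 = 13% |

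The last two rows are assumed imbalances among 30 completers. Even there, the small visible share cannot be told apart from a period effect.

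**4. What laboratory change can mean.** Section 8.3.2 allows two readings.

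- *A baseline for each period.* Period 1 change runs from screening, at Day -28 to Day -8 (section 6.1) and before the dietary washout (section 6.2). Period 2 change runs from the Visit 4 pre-dose panel of the same day. The two are different quantities.
- *One study baseline, screening.* Visit 5 change then follows both products and 176 + 25 + 185 = 386 mL of intervening draws, while Visit 3 change follows one product and 176 mL.

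Neither reading gives like-for-like changes, and the section does not choose. Vital signs do not have this problem, because they are recorded at Visits 2 and 4.

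**5. What the existing data would give.** Each completer has one 24 h value per product. For a cross-over contrast with balanced sequences, the 95% CI half-width is t(0.975, n − 2)/√n × SD, where SD is that of the within-participant difference:

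- n = 30: 0.374 × SD
- n = 36: 0.339 × SD

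The documents give no SD for any safety parameter, so this stays in SD units.

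**The case against.** The best defence is that silence is not a plan to pool. The text neither states nor excludes a product split, outcome 1 is defined by product, and a competent analyst might add the split unprompted. That is fair, and the mixing is a consequence of following the text literally, not something it announces. But nothing requires the split, and a split alone would still not supply a difference.

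The setting is also modest: an exploratory pilot with one supervised dose of each product in healthy adults, no sample size calculation and no safety hypothesis. Under section 7.1.4, clinically significant laboratory abnormalities are recorded as adverse events, so those would appear by product. This stands and limits the consequence. It does not cover shifts in means, which is what continuous summaries are for.

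A reader might also infer four stronger points that the documents do not support:

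- *That products are mixed at every visit.* No product has been taken at Visit 1 or at Visit 2 before dosing. The mixing concerns the post-dose Visits 3 and 5.
- *That the missing Visit 2 sample is why outcome 1 goes unanswered.* The 24 h values for both products exist and can be compared directly. The missing sample affects only laboratory change from baseline.
- *That the plan pools two kinds of change.* Baseline is undefined, and tables strictly by measurement point would keep Visit 3 and Visit 5 changes apart.
- *That blood loss moves the counts, and that a 24 h contrast removes this.* The documents give no such effect. Planned volume drawn before the 24 h sample is 13 + 176 = 189 mL in period 1 and 13 + 176 + 25 + 185 = 399 mL in period 2. Any cumulative effect would therefore be a period effect. It cancels only on average with balanced sequences, or with a period term.

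**Conclusion.** The point holds in two parts of unequal weight.

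The main part is that safety outcome 1 has no planned analysis. Laid out as written, the continuous safety tables would show none of a product difference at 18:18 or 15:15, and at most a small, period-confounded share under mild imbalance (13% at 17:13). This rests on reading section 8.3.2 literally and on d being additive and the same in both periods.

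The lesser part, for laboratory tests only, is that change from baseline is undefined. The only sample before the first dose is screening, while period 2 has a same-day panel.

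The primary analysis of peak plasma level and the adverse event tables are unaffected. The change should be made before the table shells are fixed. It does not call the trial's design into question.

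**What to change.** In section 8.3.2:

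1. Summarise continuous safety parameters by product and period, keeping the statistics already listed.
2. For each parameter, report the within-participant gummy-minus-caplet difference in the 24 h values from Visits 3 and 5, with a 95% CI adjusted for period. With P = Visit 3 value − Visit 5 value, the estimate is ½ × (mean P in gummy-first − mean P in caplet-first), which removes an additive period effect. Participants with both 24 h values contribute.
3. State that these intervals are descriptive and unadjusted for multiplicity.
4. State the laboratory reference for each period. Label period 1 laboratory change as change from screening, and do not combine it with change from the Visit 4 same-day sample. For vital signs, name Visit 2 and Visit 4 as the period references.

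The cost is SAP wording, some extra tables and a set of descriptive intervals, some of which will exclude zero by chance. No extra blood, visit or procedure is needed.
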